8.0 PARTICIPANT SELECTION CRITERIA

Interested participants thought to be appropriate for the study will be approached by the local Community Foot Protection Team. Following informed consent, participants will be assigned a subject ID and their status checked that they satisfy inclusion and exclusion criteria prior to admitting them to the trial. Participants will be excluded if they do not satisfy inclusion and/or exclusion criteria.

8.1 INCLUSION CRITERIA

- Participant able to give informed consent.
- Age >18 at the time of consent.
- Diagnosis of Type 1 or Type 2 Diabetes.
- Both Feet Intact (no ulceration).
- Participant understands and is willing to participate and can comply with the follow-up regime.
- Participant diabetes foot Risk Stratification as 'High Risk' as in Frame (2021) Scotland/England
<https://www.diabetesframe.org/>

- Ability to walk independently for > 100 metres i.e without use of wheelchair, walking stick or personal assistance.
- Participant able and willing to wear suitable footwear.
- Must own a mobile phone and be willing to upload WWP app.

8.2 EXCLUSION CRITERIA

- Either foot has less than 2 arterial vessel run-off on Doppler.
- Poor visual acuity ie registered blind, unless supported by carer.
- Current participation in another clinical investigation of a medical device or a drug; or participation in such a study within 30 days prior to study enrolment.
- Body Mass Index (BMI) >40.
- Participant has bespoke contact insoles and footwear.
- Participant is unable to use 'medium' or 'large' insoles due to foot size eg. small or extra large feet.
- Participant has a pacemaker.
- Participant is pregnant.

8.3 DISCONTINUATION/WITHDRAWAL OF PARTICIPANTS

The participant will remain free to withdraw at any time from the study without giving reasons and without prejudicing his/her further treatment and will be provided with a contact point where he/she may obtain further information about the study. If participants withdraw the data already collected will be anonymously utilised, but no further data will be collected.

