10.2 SCHEDULE OF EVENTS

Path Active	Screening (Pre-enrolment assessment)	Active phase 0 - 84 days.			Final visit
Visit No:	1	2		3 due to alert/concern	4
Form Number	F01, F02, F03, F04, F05	F06	F06	F07 (F09)	F08
TIMING	Pre-Assessment	Day 0 Path Active Group	Day 0 Control Group	When required	Week 12 (Day 84)
Window of flexibility for timing of visits:	- 7 days			1 day	+7 days
Randomisation		Randomisation			
Informed Consent	X				
Medical History or change to medication	X			X	
Eligibility confirmation	X			X	
Feet Assessment Neuropathy	X				
Feet Assessment Vascular Doppler	X			X	
Adverse Events review (unless reported prior to visit)				X	X
Questionnaire		X	X		X

EQ-5D-5L		X	X		X
Path Active insole fitting		X			
Daily Dashboard Review by Clinical Team		X			

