11.0 ADVERSE AND SERIOUS ADVERSE EVENTS

11.1 GENERAL DEFINITIONS

An Adverse Event (AE) is any untoward medical occurrence in a patient or a clinical trial subject which does not necessarily have a causal relationship with the device/procedure.

A Serious Adverse Event (SAE) is an untoward occurrence that:

- Is fatal
- Is life threatening
- Requires hospitalisation or prolongation of existing hospitalisation
- Results in persistent or significant disability
- Consists of a congenital anomaly or birth defect
- Is otherwise considered medically significant by the Investigator

Medical and scientific judgement must be exercised in deciding whether an event is serious. There characteristics/consequences must be considered at the time of the event and do not refer to an event which hypothetically may have caused one of the above. All potential intervention-related AEs (such as falls and consequent injuries related to wearing the insoles) will be investigated and subject to expedited reporting to the REC.

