12.0.2 Expected (S)AEs - Standard Reporting

The following AEs and SAEs are expected within the patient study population and will be reported from randomization to trial completion on standard Case Report Forms (CRFs) where the device is not a factor in the event:

- Death
- Hospital admission

- Institutionalisation

As these events are expected within the study population they will not be subject to expedited reporting to the main REC.

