12.2 RESPONSIBILITIES

Community Foot Protection Team:

- Checking for SAEs when participants attend following an alert from Path Active or there is concern from either Path Active Group or Control Group participants
- Judgement in assigning:
 - Seriousness
 - Relatedness
 - Expectedness
- To ensure all SAEs are recorded and reported to the CI within 24 hours of becoming aware and to provide further follow-up information as soon as available.

CI or delegate:

- Assign relatedness and expected nature of SAEs where it has not been possible to obtain local assessment.
- Undertake SAE review.
- Review all events assessed as Related / Unexpected in the opinion of the CI prior to reporting to the main REC.

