15.1.2 SECONDARY ENDPOINTS

- At end of study review all alerts from Path Active and responses to the alerts. Was ulceration prevented? Were there any conflicting outcomes from device use?

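### Section 8.3 ends all data collection at withdrawal with no safety exception, which conflicts with 11.1 and 12.2, cuts off follow-up of possible device harm and may miss an unreported event

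*Protocol*

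**What the plan says.** Protocol section 8.3 lets a participant leave freely ("free to withdraw at any time from the study without giving reasons") and then sets the data rule: "If participants withdraw the data already collected will be anonymously utilised, but no further data will be collected". The rule names no type of data that is exempt.

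The safety sections set duties that do not mention withdrawal:

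- Section 11.1: "All potential intervention-related AEs (such as falls and consequent injuries related to wearing the insoles) will be investigated and subject to expedited reporting".
- Section 12.2: the Community Foot Protection Team must record all SAEs, report them to the CI within 24 hours of becoming aware, and is also "to provide further follow-up information as soon as available".
- Section 12.0.2: death, hospital admission and institutionalisation, where the device played no part, "will be reported from randomization to trial completion".

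In the schedule of section 10.2, the row that begins "Adverse Events review (unless reported prior to visit" is marked in two columns only: Visit 3 (alert or concern) and Visit 4 (Week 12). There is no withdrawal column.

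**The concern.** A withdrawal rule normally separates study assessments, which stop, from safety information on events already under way, which continues as far as the participant agrees. Section 8.3 does not. Read as written, it tells a site to stop collecting at the point where 11.1 and 12.2 may require more information.

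The participants affected matter for the comparison. Only someone wearing the insoles can withdraw because the insoles caused harm, so any loss of device-related events falls on the Path Active arm and makes the device look safer than it is. Judging relatedness also needs information. Under 12.0.1 that judgement largely decides whether an event is reported at all, and it may be left unmade if enquiry stops. The secondary endpoint in 15.1.2 asks "Were there any conflicting outcomes from device use", and incomplete information on harm in people who stopped would weaken the answer.

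**Working it through.** The documents give no figure on this point, so the check compares the sections.

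**Step 1: which duties conflict with 8.3, and for which events?**

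| Section | Events covered | Duty | Conflict with 8.3 |
|---|---|---|---|
| 11.1 | Possible intervention-related AEs, serious or not | Investigate; expedited report to the REC | Yes, where investigating needs information gathered after withdrawal |
| 12.2 | All SAEs, whatever the cause | Record, report to the CI within 24 hours of awareness, follow up | Yes, for the follow-up |
| 12.0.2 | Death, admission, institutionalisation, device not a factor | Report on the CRF from randomisation to trial completion | Yes, for events after withdrawal, but these are not device harms |

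For a non-serious insole injury, 11.1 is therefore the only duty that conflicts with 8.3. For a serious one, both 11.1 and 12.2 do. Section 12.0.2 is a separate conflict about unrelated events.

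**Step 2: what is kept and what is lost?** Take a participant who falls because of an insole and withdraws on day 30.

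- *The site recorded the fall before or at withdrawal.* Section 8.3 keeps that record, and the event can be reported from data already held. Lost are any later enquiry into the cause, the course of the injury and its outcome.
- *The site had not heard of the fall.* Nothing in the protocol prompts the question. Section 10.2 has no AE review at withdrawal, 12.2 ties SAE checks to attendance after an alert or concern, and 8.3 rightly requires no reason for leaving. Unless the participant volunteers the event, it goes unrecorded.

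**Step 3: does any section settle the order of precedence?** Section 8.3 does not refer to sections 11 or 12, and those sections do not mention withdrawn participants. Section 16.0 says participants will be asked to consent to access to their medical records, but not whether that access continues after withdrawal. The conflict is left to each site to resolve.

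**The case against.** The best reply is that little would be lost in practice. Data already collected are retained. The schedule allows AEs to be reported outside visits, and a concern raised by a participant in either group leads to a Visit 3 with an AE review. The duties in 12.2 depend on the site becoming aware and on information being available. The team that checks for SAEs is also the participant's usual foot care team, and leaving the study does not affect further treatment.

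Much of this stands, and it rules out several stronger readings:

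- A reader might infer that anyone who leaves after an insole injury vanishes from the safety record. Section 8.3 itself says otherwise: what was recorded stays.
- A reader might count 12.0.2 among the duties to follow device harm. It covers only events in which the device is not a factor.
- A reader might say that nobody is assigned to complete the enquiry. For SAEs, 12.2 gives assessment and follow-up to the local team and review to the CI.
- The link to the endpoint in 15.1.2 is an inference. That endpoint begins from a review of alerts and does not mention AEs.
- A reader might want a percentage of events missed. Any such figure comes from its inputs. Assume 60 device users, an AE risk of 5% in stayers and 30% in leavers, and no leaver's event recorded. Then 10% withdrawal gives 6 × 0.30 = 1.8 missed of 54 × 0.05 + 1.8 = 4.5 events (40%), and 20% withdrawal gives 12 × 0.30 = 3.6 of 48 × 0.05 + 3.6 = 6.0 (60%). If half the leavers' events are recorded first, this becomes 20% to 30%. With equal 5% risk and none recorded, it is 10% to 20%. If all are recorded first, it is zero. None of these inputs is in the protocol.

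The reply does not remove the conflict over information gathered after withdrawal, or the missing AE review at withdrawal. Goodwill in the usual clinic does not override a written rule against collecting further data.

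**Conclusion.** The point holds in a limited form. Section 8.3, followed as written, conflicts with 11.1 for possible device-related AEs and with 12.2 for follow-up of SAEs. The consequence is loss of later investigation and outcome for recorded events, and possible loss of events not yet reported when the participant leaves. For device-related harm, that loss can arise only in the Path Active arm. The 12.0.2 window also conflicts with 8.3, but for unrelated events and in both arms.

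No magnitude can be derived, because the protocol gives no withdrawal rate and no AE rate. The conclusion rests on the text alone. The participant information and consent wording are not in the material at hand, so whether they already permit safety follow-up after withdrawal cannot be judged. The point should be corrected because the sections contradict each other and the remedy is cheap; it does not show that the safety data will be seriously incomplete.

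**What to change.** Reconcile 8.3 with 11.1, 12.2 and the 12.0.2 window. State in 8.3 that withdrawal ends study visits and questionnaires, and that:

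1. an AE review is offered at the contact at which the participant withdraws, with a matching withdrawal column in the 10.2 schedule;
2. possible device-related AEs, and any SAEs, with onset up to withdrawal continue to be followed and reported under 11.1 and 12.2, within the consent given;
3. events under 12.0.2 either are or are not still reported after withdrawal, with the choice written down and the 12.0.2 window worded to match.

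Check that the participant information agrees with the revised text; it may already do so.

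The cost is a short protocol amendment and a few minutes at the withdrawal contact. Some participants will decline even safety follow-up. That must be respected and recorded as a refusal, and giving a reason for leaving stays voluntary.

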9.0 PARTICIPANT RECRUITMENT PROCESS

The study will only commence once evidence of the following approval/essential documents are in place:

1. The main REC approval (if applicable),
2. HRA approval
3. Final sponsorship and host site confirmation of capacity and capability

All participants who wish to enter the study will be approached by the local Community Foot Protection Team and written consent taken. Potential participants will have the opportunity to ask any questions they have prior to giving consent. Patient information sheets will be available as part of the consenting process.

10.0 STUDY PROCEDURES

10.1 INFORMED CONSENT

Informed consent from the participant will be obtained in clinic following provision of written information to the potential participant. Any queries the potential participant may have should be addressed by delegated and trained members of the local study team.

The information supplied to the potential participant will include a statement that they are under no obligation to enter the trial and that they can withdraw at any time, without having to give a reason.

10.2 SCHEDULE OF EVENTS

Path Active	Screening (Pre-enrolment assessment)	Active phase 0 - 84 days.			Final visit
Visit No:	1	2		3 due to alert/concern	4
Form Number	F01, F02, F03, F04, F05	F06	F06	F07 (F09)	F08
TIMING	Pre-Assessment	Day 0 Path Active Group	Day 0 Control Group	When required	Week 12 (Day 84)
Window of flexibility for timing of visits:	- 7 days			1 day	+7 days
Randomisation		Randomisation			
Informed Consent	X				
Medical History or change to medication	X			X	
Eligibility confirmation	X			X	
Feet Assessment Neuropathy	X				
Feet Assessment Vascular Doppler	X			X	
Adverse Events review (unless reported prior to visit)				X	X
Questionnaire		X	X		X

EQ-5D-5L		X	X		X
Path Active insole fitting		X			
Daily Dashboard Review by Clinical Team		X			

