4.0 STUDY FLOW CHART

5.0 INTRODUCTION

5.1 BACKGROUND

More than 4.9M people have been diagnosed with diabetes (DM) in the UK, and up to 25% (1.2M) will develop a Diabetic Foot Ulcer (DFU) in their lifetimes. 15-20% of DFUs lead to amputations which are followed by significantly increased mortality. The cost to taxpayers is enormous (Kerr 2019), consuming 1% of NHS budget annually.

The current method of providing periodic foot checks is inadequate, with the chance of recurrence of an ulcer being 40% in the first year, rising to almost 100% over 10 years (Armstrong 2017). Individuals at high risk of DFU go to clinic to have their feet checked at least once a month. This can be highly disruptive to their everyday lives. Furthermore, there is considerable environmental cost of patient travel and if a DFU occurs single-use consumables for treatment such as dressings, bandages, scalpels, blood tests, cultures for microbiology , etc.

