6.0 RESEARCH QUESTIONS

- Is Path Active as effective as regular routine podiatry review in foot ulcer prevention?
- Does using Path Active improve participant QoL?
- Are there any suggestions from participants to improve the device/app?
- Will preventing foot ulceration reduce NHSE carbon footprint?

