7.0 TRIAL DESIGN

7.1 METHOD

Study setting

Participants who have been assessed as having a 'high risk' of foot ulceration will be recruited from Community Foot Protection Teams in 4 sites across the UK. Participants will be recruited to the study to a maximum total of 120 (30 at each site) who have completed the study. The number of recruits required is based on a power calculation for the study at the 95% confidence interval.

The study is anticipated to run for 12 months.

Procedure

Potential participants will be approached to participate during routine review by the Community Foot Protection Teams and consented by them for the study. All participants will be screened at pre-assessment by the Community Foot Protection Teams.

Following completion of informed consent the participant will have;

- Medical History
- Arterial Doppler scan

- Test for Neuropathy
- Eligibility confirmation
- EuroQoL Assessment (EQ-5D-5L)
- Patient Questionnaire
- Randomised to 'Path Active Group' or 'Control Group' using computer randomisation.

If the participant is randomised to use the device in the 'Path Active Group';

- Participant Training in device and mobile app use (Appendix 1).

If there is an alert from Path Active app the participant will be asked to reduce walking and rest their feet. If the alert continues and activates the clinical dashboard, patients will be contacted to attend clinic for review.

If the participant is not randomised to use the device in the 'Control Group', they will continue with their regular podiatry clinical reviews with the Community Foot Protection Team who will provide their standard of care.

Day 84 (week 12). At the end of study;

- EuroQoL Assessment (EQ-5D-5L)
- Patient Questionnaire

If the participant is randomised to use the device;

- Device retained by clinical research team.

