15.2 ANALYSIS PLANS

15.2.1 PRIMARY ENDPOINT ANALYSIS

Day 84; Data will be analysed to determine the effectiveness of 'Path Active' compared with standard podiatry review.

Questionnaires will be reviewed for QoL outcomes and patient experience.

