15.2.2 SECONDARY ENDPOINT ANALYSIS

Day 84; Alerts from Path Active will be analysed to assess a base level of sensitivity and specificity.

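### No explicit ulcer check is scheduled after enrolment, and none at Day 84, so ulcer ascertainment may differ by arm in an unknown direction

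*Protocol*

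**What the plan says.** Four parts of the protocol depend on knowing who ulcerated.

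- Section 6.0 asks "Is Path Active as effective as regular routine podiatry review in foot ulcer prevention".
- Section 15.2.1 plans a Day 84 analysis of effectiveness "compared with standard podiatry review".
- Section 15.1.2 asks, as a secondary endpoint, whether ulcers were prevented. Section 15.2.2 adds that "Alerts from Path Active will be analysed to assess a base level of sensitivity and specificity".
- Section 15.1.1 lists among the primary endpoints a model of the carbon saving from ulcers avoided.

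The schedule in 10.2 has two foot rows: neuropathy at Visit 1, and Doppler at Visits 1 and 3. Neither is marked at the final visit. The final visit carries adverse event review, the questionnaire and EQ-5D-5L, and the Day 84 list in 7.1 has no foot examination. The only study visit between Day 0 and Day 84 is "3 due to alert/concern".

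On contact during follow-up, 7.1 says for the device arm "If there is an alert from Path Active app the participant will be asked to reduce walking and rest their feet", and then "If the alert continues and activates the clinical dashboard, patients will be contacted to attend clinic for review". For controls it says "they will continue with their regular podiatry clinical reviews with the Community Foot Protection Team who will provide their standard of care".

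**The concern.** A comparison of ulcer occurrence is fair only if ulcers are found and recorded in the same way in both arms. Here the protocol sets no common look at the feet after enrolment, and at least one route to the clinic exists in one arm only. Whether an ulcer reaches the dataset could then depend on how closely each arm is watched as well as on whether it occurred. The comparison could show a difference where there is none, or hide a real one. The alert analysis is exposed too, because sensitivity and specificity need ulcer status for every device user, including those who never had an alert.

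This concerns what is collected at visits. A statistical analysis plan cannot repair it later, and an ulcer that healed unrecorded may not be recoverable. The questionnaire and EQ-5D-5L results are not affected.

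**Working it through.** **1. Where could an ulcer be recorded?**

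| Route | Device arm | Control arm | Dependable for ulcers? |
|---|---|---|---|
| Day 84 visit (7.1, 10.2) | yes | yes | No foot or ulcer row |
| Visit 3 after an alert (7.1, 10.2) | yes | not possible | Implied: the eligibility row is marked, and 8.1 requires intact feet |
| Visit 3 after a concern (10.2, 12.2) | yes | yes | Same implied check, only for those who attend |
| Daily dashboard review (10.2) | yes | no | Can only lead to a visit |
| Routine podiatry (7.1) | not stated | continues | No stated route from clinic finding to study record |
| Adverse event review at Visits 3 and 4 (10.2) | yes | yes | Limited by 12.0.1 and 12.0.2 |

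On the last row, 12.0.1 leaves events unreported unless judged related, and 12.0.2 adds back only death, hospital admission and institutionalisation. An outpatient ulcer judged unrelated falls outside both. A control participant has no device for an ulcer to be related to, so this filter can itself act differently by arm.

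**2. Direction.** Alert visits add looks in the device arm. Routine reviews add looks in the control arm if device users have fewer of them. Section 5.1 says "Individuals at high risk of DFU go to clinic to have their feet checked at least once a month", which over the study is 84/30.4 = 2.8, or about 3 checks. Section 5.2 expects the device to lower the need for visits. Neither section sets visits for this trial, so the net direction cannot be derived.

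**3. Size, for illustration.** The protocol gives no figure for ascertainment to reproduce. The recording shares below are assumptions.

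With equal true risk, apparent risk ratio = (share recorded in one arm) / (share recorded in the other).

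- 90% and 70%: 0.90/0.70 = 1.29, or 0.70/0.90 = 0.78 if the arms are swapped.
- 95% and 85%: 0.95/0.85 = 1.12, or 0.89 if swapped.
- Equal shares: 1.00.

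**4. In numbers of ulcers.** Inputs: 40% recurrence in the first year (5.1) and 120 completers (7.1). Assumptions: constant hazard, 60 per arm (the allocation ratio is not stated), and a recurrence rate applied to people for whom a previous ulcer is not an entry criterion.

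- Risk over 84 days = 1 − 0.60^(84/365) = 11.1%.
- Expected ulcers per arm = 60 × 0.111 = 6.7.
- Recorded at 90%: 6.0. Recorded at 70%: 4.7. The gap is about 1.3 ulcers.

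With so few events, one or two unrecorded ulcers are enough to move the ratio this far.

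**The case against.** Several points on the other side are fair.

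- *An ulcer check does exist after enrolment.* A reader might infer from the schedule that there is none at all. The documents do not support that. Visit 3 repeats the eligibility confirmation, and 8.1 includes intact feet, so a check is implied there. It reaches only those who attend on an alert or concern, and the row is not marked at Day 84.
- *The final adverse event review covers both arms, and 11.1 defines an adverse event broadly enough to include an ulcer.* True, and some ulcers may be captured this way. The reporting limits in 12.0.1 and 12.0.2 still make it undependable. Section 12.2 asks for all serious events to be recorded, which conflicts with 12.0.1. That conflict is a separate point.
- *Forms F07 to F09, the questionnaire and the flow chart are not shown.* This stands. If F08 records ulcer status, the Day 84 gap shrinks to a missing line in the schedule.
- *Routine podiatry may continue in the device arm.* This also stands. A reader might infer that it stops, but 7.1 is silent, and 5.1 and 5.2 are background. What is established is that alerts and dashboard review exist in one arm only.
- *Medical records could be searched.* Section 16.0 seeks consent for access, but in the context of monitoring and audit. It is not a planned outcome source applied equally to both arms.

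A reader might also infer a known bias in alert sensitivity. That is not supported. Missing ulcers without an alert would raise it, while ulcers averted by alert-driven rest lower it. The second effect is not a matter of ascertainment: with true sensitivity 0.50, half of the alert-preceded ulcers averted and every ulcer recorded, the result is 0.25/(0.25 + 0.50) = 0.33. Better recording does not remove that error, so the analysis needs the right label as well as better data.

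**Conclusion.** The concern holds in this form: the lead research question, the Day 84 effectiveness comparison, the secondary ulcer endpoint and the carbon model all need ulcer occurrence in both arms, but no explicit ulcer check is scheduled after enrolment and none at Day 84. Ascertainment may differ by arm. That is a risk created by the plan as written, not a demonstrated bias, and the documents do not support saying which arm it would favour.

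The illustrative size is an apparent risk ratio of 1.29 or 0.78 under equal true risk, from a gap of about 1.3 ulcers. This rests on assumed recording shares of 90% and 70%, a constant hazard taken from a recurrence figure, and 60 participants per arm. The structural finding does not depend on any of these numbers. It does depend on the unseen forms, F08 above all. It is best treated as a cheap improvement to make before data collection.

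**What to change.** - Add a row to 10.2, *Ulcer status, both feet (yes/no, site, date)*, at Week 12 (F08) and Visit 3 (F07) for both arms, using one written ulcer definition. If F08 already carries this, show it in the schedule.
- On the CRF, record any ulcer since Day 0, wherever it was found and regardless of relatedness. Ulcers that healed before Day 84 then count, and capture no longer depends on the adverse event rules.
- State in 7.1 whether routine podiatry reviews continue in the device arm, and record the number of foot checks per participant in both arms.
- Compute alert sensitivity and specificity against this ulcer status for all device-arm participants, with or without an alert, and label the result as performance under alert-driven care.
- Reconcile 12.0.1 and 12.0.2 with 12.2 on which events are recorded, as a separate point.

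The cost is one schedule row, a few CRF fields and a few minutes at visits that already take place. Extra looks from alert visits remain, so the imbalance is reduced and not removed. The count of foot checks makes what remains visible.
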